### 11.3.3 Measurement at Follow-up Evaluation:

The cytological confirmation of the neoplastic origin of any effusion that appears or worsens during treatment when the measurable tumor has met criteria for response or stable disease is mandatory to differentiate between response or stable disease (an effusion may be a side effect of the treatment) and progressive disease.

Cytologic and histologic techniques can be used to differentiate between PR and CR in rare cases (e.g., residual lesions in tumor types such as germ cell tumors, where known residual benign tumors can remain.)

## 11.4 Measurement of Treatment/Intervention Effect

### 11.4.1 Target Lesions & Target Lymph Nodes

- The protocol defined irradiated tumor will not be considered for response in the primary endpoint.
- The protocol defined irradiated tumor will be considered for secondary endpoint response.
- Measurable lesions (as defined in [Section 11.2.1](#)) up to a maximum of 5 lesions, representative of all involved organs, should be identified as “Target Lesions” and recorded and measured at baseline. These lesions can be non-nodal or nodal (as defined in [Section 11.2.1](#)), where no more than 2 lesions are from the same organ and no more than 2 malignant nodal lesions are selected.
- Note: If fewer than 5 (for phase III trials replace with “3”) target lesions and target lymph nodes are identified (as there often will be), there is no reason to perform additional studies beyond those specified in the protocol to discover new lesions.
- Target lesions and target lymph nodes should be selected on the basis of their size, be representative of all involved sites of disease, but in addition should be those that lend themselves to reproducible repeated measurements. It may be the case that, on occasion, the largest lesion (or malignant lymph node) does not lend itself to reproducible measurements in which circumstance the next largest lesion (or malignant lymph node) which can be measured reproducibly should be selected.
- Baseline Sum of Dimensions (BSD): A sum of the longest diameter for all target lesions plus the sum of the short axis of all the target lymph nodes will be calculated and reported as the baseline sum of dimensions (BSD). The BSD will be used as reference to further characterize any objective tumor response in the measurable dimension of the disease.

- Post-Baseline Sum of the Dimensions (PBSD): A sum of the longest diameter for all target lesions plus the sum of the short axis of all the target lymph nodes will be calculated and reported as the post-baseline sum of dimensions (PBSD). If the radiologist is able to provide an actual measure for the target lesion (or target lymph node), that should be recorded, even if it is below 0.5 cm. If the target lesion (or target lymph node) is believed to be present and is faintly seen but too small to measure, a default value of 0.5 cm should be assigned. If it is the opinion of the radiologist that the target lesion or target lymph node has likely disappeared, the measurement should be recorded as 0 cm.
- The minimum sum of the dimensions (MSD) is the minimum of the BSD and the PBSD.
- 

#### 11.4.2 Non-Target Lesions & Non-Target Lymph Nodes

Non-measurable sites of disease ([Section 11.2.2](#)) are classified as non-target lesions or non-target lymph nodes and should also be recorded at baseline. These lesions and lymph nodes should be followed in accord with 11.4.3.3.

#### 11.4.3 Response Criteria

All target lesions and target lymph nodes followed by CT/MRI/PET-CT/Chest X-ray/physical examination must be measured on re-evaluation at evaluation times specified in [Section 11.1](#). Specifically, a change in objective status to either a PR or CR cannot be done without re-measuring target lesions and target lymph nodes.

**Note:** Non-target lesions and non-target lymph nodes should be evaluated at each assessment, especially in the case of first response or confirmation of response. In selected circumstances, certain non-target organs may be evaluated less frequently. For example, bone scans may need to be repeated only when complete response is identified in target disease or when progression in bone is suspected.

- Evaluation of Target Lesions
  - Complete Response (CR): All of the following must be true:
    - Disappearance of all target lesions.
    - Each target lymph node must have reduction in short axis to < 1.0 cm.
  - Partial Response (PR): At least a 30% decrease in PBSD (sum of the longest diameter for all target lesions plus the sum of the short axis of all the target lymph nodes at current evaluation) taking as reference the BSD (see [Section 11.4.1](#)).
  - Progression (PD): At least one of the following must be true:
    - At least one new malignant lesion, which also includes any lymph node that was normal at baseline (< 1.0 cm short axis) and increased to  $\geq 1.0$  cm short axis during follow-up.
    - At least a 20% increase in PBSD (sum of the longest diameter for all target lesions plus the sum of the short axis of all the target lymph nodes at current evaluation) taking as reference the MSD (Section 11.4.1). In addition, the PBSD must also demonstrate an absolute increase of at least 0.5 cm from the MSD.

- See [Section 11.3.2](#) for details in regards to the requirements for PD via FDG-PET imaging.
    - Stable Disease (SD): Neither sufficient shrinkage to qualify for PR, nor sufficient increase to qualify for PD taking as reference the MSD.
  - Evaluation of Non-Target Lesions & Non-target Lymph Nodes
    - Complete Response (CR): All of the following must be true:
      - Disappearance of all non-target lesions.
      - Each non-target lymph node must have a reduction in short axis to <1.0 cm.
    - Non-CR/Non-PD: Persistence of one or more non-target lesions or non-target lymph nodes.
    - Progression (PD): At least one of the following must be true:
      - At least one new malignant lesion, which also includes any lymph node that was normal at baseline (< 1.0 cm short axis) and increased to  $\geq 1.0$  cm short axis during follow-up.
      - Unequivocal progression of existing non-target lesions and non-target lymph nodes. (NOTE: Unequivocal progression should not normally trump target lesion and target lymph node status. It must be representative of overall disease status change.)
      - See [Section 11.3.2](#) for details in regards to the requirements for PD via FDG-PET imaging.
  - Evaluation of Elevated Hormone Levels (when present)
    - This evaluation will be done for each patient for descriptive purposes only and will not be used to evaluate the primary endpoint of objective response. Biochemical progression without the demonstration of objective progression of target or nontarget lesion will not be sufficient indication to remove the patient from the study (refer to Section 13.1).
    - Biochemical response (B-RESP): Reduction in elevated hormone level by at least 50% of normalization of an elevated value, confirmed with 2 successive measures.
    - Biochemical progression (B-PROG): Increase in elevated hormone level by 50%, confirmed with 2 successive measures. If patient has had biochemical response as defined above, then subsequent biochemical progression is defined as >50% increase from the lowest recorded level while on study.
    - Biochemical stability (B-STAB): Elevated hormone level does not change enough to qualify as response or progression.

#### 11.4.4 Overall Objective Status

The overall objective status for an evaluation is determined by combining the patient's status on target lesions, target lymph nodes, non-target lesions, non-target lymph nodes, and new disease as defined in the following tables:

For Patients with Measurable Disease

Target Lesions & Target Lymph Nodes	Non-Target Lesions & Non-Target Lymph Nodes	New Sites of Disease	Overall Objective Status
CR	CR	No	CR
CR	Non-CR/Non-PD	No	PR
PR	CR Non-CR/Non-PD	No	PR
CR/PR	Not All Evaluated*	No	PR
SD	CR Non-CR/Non-PD Not All Evaluated*	No	SD
Not all Evaluated	CR Non-CR/Non-PD Not All Evaluated*	No	Not Evaluated (NE)
PD	Unequivocal PD CR Non-CR/Non-PD Not All Evaluated*	Yes or No	PD
CR/PR/SD/PD/Not all Evaluated	Unequivocal PD	Yes or No	PD
CR/PR/SD/PD/Not all Evaluated	CR Non-CR/Non-PD Not All Evaluated*	Yes	PD

\* See Section 11.4.3.1

#### 11.4.5 Symptomatic Deterioration

Patients with global deterioration of health status requiring discontinuation of treatment without objective evidence of disease progression at that time, and not either related to study treatment or other medical conditions, should be reported as PD due to “symptomatic deterioration.” Every effort should be made to document the objective progression even after discontinuation of treatment due to symptomatic deterioration.

#### 11.5 Immune-Related Response Assessment (iRECIST)

All study endpoints requiring measurement data will be assessed per RECIST criteria (defined above). Patients will not be required to end study participation at the first evidence of progression since Immunotherapeutics may result in infiltration of immune cells leading to transient increase in the size of malignant lesions, or undetectable lesions becoming detectable. For this reason, iRECIST [24] will be utilized in order to help to make the decision to remove a patient from the study after first evidence of progression. The criteria are identical to those of RECIST 1.1 in many respects but have been adapted to account for instances where an increase in tumor burden, or the appearance of new lesions, does not reflect true tumor progression. Key differences are described below. All responses defined using iRECIST criteria are designated with a prefix.

##### 11.5.1 Confirming Progression

Unlike RECIST 1.1, iRECIST requires the confirmation of progression and uses the terms iUPD (unconfirmed progression) and iCPD (confirmed progression). Confirmatory scans should be performed at least 4 weeks, but not longer than 9 weeks after iUPD.

For patients that had an iUPD in the previous assessment, iCPD is confirmed in two ways:

- Existing iUPD gets worse in any lesion type (target, non-target, or new lesions) which contributed to the current iUPD status (a patient can have more than one of the following sources of iUPD).

If iUPD was at least partially based on...	Then iCPD is confirmed if...
Target lesions	A cumulative increase (can occur over multiple assessments) of at least 5 mm in the absolute value of the sum from the first occurrence of the current iUPD
Non-target lesions	Any increase in the non-target lesion burden from the first occurrence of the current iUPD
New lesions	A cumulative increase (can occur over multiple assessments) of at least 5 mm in the absolute value of the sum of those considered to be target new lesions or any new lesions (from the first occurrence of the current iUPD)

- RECIST 1.1 criteria are met in lesion types (target, non-target, or new lesions) which did not contribute to current iUPD status, including the appearance of new lesions.

If a patient meets either (or both) of these criteria, they are considered to have confirmed progression (iCPD). See Appendix III for examples of confirming progression.

### 11.5.2 New Lesions

New lesions should be assessed and measured as they appear using RECIST 1.1 criteria, and recorded as New Lesion-Target (NLT) and New Lesion-Non-Target (NLNT) to allow clear differentiation from baseline target and non-target lesions.

New lesions may either meet the criteria of NLT or NLNT to drive iUPD (or iCPD). However, the measurements of NLT should NOT be included in the sum of measures of original target lesions identified at baseline.

Progression is confirmed in the New Lesion category if the next imaging assessment, conducted at least 4 weeks (but not more than 9 weeks) after iUPD confirms further progression from iUPD with either an increase of at least 5 mm in the absolute value of the sum of NLT OR and increase (but not necessarily unequivocal increase) in the size of NLNT lesions OR the appearance of new lesions.

The following table summarizes how to use iRECIST in a number of different scenarios.

Target Lesions*	Non-Target Lesions*	New Lesions*	Time Point Response	
			No prior iUPD**	Prior iUPD**, ***
iCR	iCR	No	iCR	iCR
iCR	Non-iCR/Non-iUPD	No	iPR	iPR

iPR	Non-iCR/Non-iUPD	No	iPR	iPR
iSD	Non-iCR/Non-iUPD	No	iSD	iSD
iUPD with no change OR decrease from last TP	iUPD with no change OR decrease from last TP	Yes	NA	NLs confirms iCPD if NLs were previously identified and increase in size ( $\geq 5$ mm in SOM for NLT or any increase for NLNT) or number. If no change in NLs (size or number) from last TP, remains iUPD
iSD	iUPD	No	iUPD	Remains iUPD unless iCPD confirmed based in further increase in size of NT disease (need not meet RECIST 1.1 criteria for unequivocal PD)
iUPD	Non-iCR/Non-iUPD	No	iUPD	Remains iUPD unless iCPD confirmed based on: - further increase in SOM of at least 5 mm, otherwise remains iUPD
iUPD	iUPD	No	iUPD	Remains iUPD unless iCPD confirmed based on further increase in: - previously identified T lesion iUPD SOM $\geq 5$ mm and / or - NT lesion iUPD (prior assessment - need not be unequivocal PD)
iUPD	iUPD	Yes	iUPD	Remains iUPD unless iCPD confirmed based on further increase in: - previously identified T lesion iUPD $\geq 5$ mm and / or - previously identified NT lesion iUPD (need not be unequivocal) and /or - size or number of new lesions previously identified
Non-iUPD/PD	Non-iUPD/PD	Yes	iUPD	Remains iUPD unless iCPD confirmed based on - increase in size or number of new lesions previously identified

* Using RECIST 1.1 principles. If no PSPD occurs, RECIST 1.1 and iRECIST categories for CR, PR and SD would be the same.
 
** In any lesion category.
 
*** Previously identified in assessment immediately prior to this TP.
				

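### The iUPD/iUPD/Yes row of the 11.5.2 iRECIST table omits the second route to confirmed progression in 11.5.1, so a first new lesion can stay at iUPD where 11.5.1 gives iCPD

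*Combined protocol and SAP*

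**What the plan says.** Section 11.5.1 of the combined protocol and SAP sets out two ways in which an iUPD becomes an iCPD.

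- Criterion 1 is worsening in a lesion type that contributed to the current iUPD. For target lesions this is a cumulative rise of "at least 5 mm in the absolute value of the sum from the first occurrence of the current iUPD". For non-target lesions any increase counts.
- Criterion 2 is RECIST 1.1 progression in lesion types "which did not contribute to current iUPD status, including the appearance of new lesions".

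One criterion is enough: "If a patient meets either (or both) of these criteria, they are considered to have confirmed progression (iCPD"). The sentence directly above the 11.5.2 table also counts new lesions appearing among the findings that confirm progression in the new-lesion category.

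The 11.5.2 table then summarises a set of scenarios. Footnote ** to its prior-iUPD column says that the earlier iUPD may lie in any lesion category. In the iUPD/iUPD/Yes row (target iUPD, non-target iUPD, new lesions present), that column leaves the patient at iUPD unless there is a further increase in one of three things: previously identified target iUPD by at least 5 mm, or "previously identified NT lesion iUPD (need not be unequivocal) and /or - size or number of new lesions previously identified". A separate row covers target and non-target disease that are each "iUPD with no change OR decrease from last TP", again with new lesions present.

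Appendix III example 3 has target sums of 100, 125 and 125, unchanged non-target disease and one new lesion at the last scan. It is scored iCPD and attributed to criterion 2.

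**The concern.** All three routes in the iUPD/iUPD/Yes cell are forms of criterion 1, and criterion 2 is absent. A lesion seen for the first time at the current scan was not previously identified, so on a literal reading it cannot confirm progression in this row. Under 11.5.1 it does, provided new lesions played no part in the current iUPD. The same scan therefore gets two statuses from adjoining subsections.

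The status matters because 12.1.2 takes patients with confirmed progression off protocol therapy and lets clinically well patients go on after RECIST progression only while iCPD is not met. A site that reads the status from the table could keep treating a patient whom 11.5.1 classes as confirmed.

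**Working it through.** **Check of the 11.5.1 rule against Appendix III** (sums in mm; rise measured from the first iUPD at 125)

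- Example 1: 132 − 125 = 7, at least 5, so iCPD, as printed.
- Example 2: 128 − 125 = 3, under 5, so iUPD; then 132 − 125 = 7, so iCPD. Both as printed.
- Example 3: 125 − 125 = 0, but a first new lesion, so iCPD by criterion 2, as printed.
- Example 4: 132 − 125 = 7 plus a new lesion, so iCPD. This matches the example's heading; its final table row is cut off in the text.

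**Worked case for the row.** Use the first three sums of example 2 (100, 125, 128). Let non-target disease also reach iUPD at the second scan. At the third scan non-target disease has not increased and a first new lesion is seen.

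1. Second scan: (125 − 100)/100 = 25%, and 25 mm. Both exceed the 20% and 0.5 cm thresholds of 11.4.3, so the target is iUPD.
2. Third scan: (128 − 100)/100 = 28%, and 28 mm over the minimum of 100. The target is still iUPD.
3. Rise since first iUPD: 3 mm. This is under the 5 mm needed to confirm. It is above 0, so the row for unchanged or decreased disease does not fit.
4. The row that fits is iUPD/iUPD/Yes. Its three routes are target rise of at least 5 mm (no), non-target increase (no), and increase in previously identified new lesions (there were none). Result: iUPD.
5. Criterion 2: new lesions did not contribute to the current iUPD, and one has appeared. Result: iCPD.

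**Where the row and the rule agree and differ**

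| Source of prior iUPD | This scan | Row, read literally | 11.5.1 |
|---|---|---|---|
| Target + non-target | First new lesion, target +3 mm, no non-target increase | iUPD | iCPD |
| Target + non-target | First new lesion, target +3 mm, non-target increase | iCPD | iCPD |
| Target + non-target | First new lesion, target +5 mm or more | iCPD | iCPD |
| Target + non-target + new lesions | A further new lesion | iCPD | iCPD |
| New lesions only | First target and non-target progression, new lesions unchanged | iUPD | iCPD |

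The last line is the same omission in reverse. No target or non-target iUPD was previously identified, so the cell has nothing to measure an increase against, yet criterion 2 is met.

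**Exposure per discordant call.** Pembrolizumab is 200 mg every 3 weeks (7.0). For scan timing, 11.5.1 says: "Confirmatory scans should be performed at least 4 weeks, but not longer than 9 weeks after iUPD". Assume that this interval also applies to the scan after a discordant call, and that dosing starts on the day of that call.

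- Rescan at 4 weeks: doses at weeks 0 and 3, so 2 × 200 = 400 mg.
- Rescan at 9 weeks: doses at weeks 0, 3 and 6, so 3 × 200 = 600 mg.

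**The case against.** The strongest reply is that the protocol already gives the right answer. Section 11.5.1 states the rule, the sentence above the table names new lesions appearing, and Appendix III works a close analogue. The table is only a summary, and its default yields to confirmation, a term that 11.5.1 defines. This stands as a limit on the harm: a site that reads the whole section will classify correctly. It does not make the cell correct, because the cell goes on to list the grounds for confirmation and leaves one out.

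A second reply is that the cell's reference to number could cover a change from no new lesions to one. Taken strictly, a set already identified cannot grow in number, so this reading has some force. But the cell asks for a further increase and ties it to lesions previously identified, and footnote *** uses that phrase for the assessment immediately before. The wording leans against a count that starts from zero.

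A third reply is that a 3 mm rise might pass as no change, which would move the worked case to the neighbouring row. That row sets new-lesion growth of at least 5 mm against no change, which gives the idea some support. Appendix III example 2, however, describes the path through 128 as gradual continuing growth, so 128 after 125 is not unchanged.

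A reader might also infer that the neighbouring row contradicts 11.5.1. The documents do not go that far. It says "NLs confirms iCPD if NLs were previously identified and increase in size", which leaves out a first new lesion, but also "If no change in NLs (size or number) from last TP, remains iUPD", which does not hold such a patient at iUPD. It is ambiguous, not contradictory. Nor does the point extend to the Non-iUPD/PD/Yes row: there an earlier iUPD may have resolved, and the new lesion may be a fresh iUPD.

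Finally, Appendix III example 3 is not an instance of the disputed row, because its non-target disease is present but not in iUPD. It supports criterion 2 by analogy. Its own pattern has no row in the table, which is a gap and not a conflict.

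**Conclusion.** The point holds as an inconsistency of narrow reach. The prior-iUPD cell of the iUPD/iUPD/Yes row covers criterion 1 only. For a first new lesion, the clear conflict needs all of the following: a prior iUPD from target and non-target disease but not new lesions, target growth above 0 but under 5 mm since that iUPD, and no non-target increase. Low target growth alone is not enough, because any non-target increase confirms in that row. The reverse case, after an iUPD from new lesions only, is also missed.

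A reader might infer that primary PFS or the design is affected. Section 11.5 rules this out: all measurement endpoints use RECIST, and 13.2.1 dates the PFS event at first evidence of progression, without iRECIST confirmation. A reader might also infer that patients were over-treated. The documents do not show that any patient met the pattern, and the number cannot be derived from them. The 2 to 3 doses are a per-call figure under the timing assumptions above. Section 12.1.2 permits continuation but does not require it, 11.5 uses iRECIST only to help the decision, and treatment is capped at two years. The update notice at the front of the protocol says that accrual is closed, so the point concerns patients still on treatment and the reading of past removal decisions.

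**What to change.** In the prior-iUPD cells of the iUPD/iUPD/Yes row and of the row for unchanged or decreased disease with new lesions, add: *or RECIST 1.1 progression in a lesion type that did not contribute to the current iUPD, including the first appearance of new lesions (criterion 2 of 11.5.1)*. State beneath the table that 11.5.1 governs where the two differ. The general wording is needed because a clause limited to new lesions would leave the reverse case uncorrected.

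Optionally add a row for target iUPD, Non-iCR/Non-iUPD and new lesions Yes. Its prior-iUPD cell should say to apply both criteria of 11.5.1. Pointing only to the table in 11.5.1 would repeat the omission, since that table holds criterion 1 alone. Leave the Non-iUPD/PD/Yes row as it is.

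The cost is one clause in two cells, one sentence and, if wanted, one row. Data collection, endpoints and analysis do not change.

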## 11.6 Definitions of Analysis Variables

Formal definitions of variables used in analyses can be found in the Statistical Considerations section of the protocol.

## 12.0 END OF TREATMENT/INTERVENTION

### 12.1 Duration of Treatment

#### 12.1.1 CR, PR, or SD

Patients who are in CR, PR or SD will continue on therapy for a total of two years of treatment. After treatment is discontinued, patients will be followed per the study calendar in [section 5.0](#).

#### 12.1.2 Disease Progression

Remove from protocol therapy any patient with confirmed disease progression. Document details, including tumor measurements, on data forms. Patients who are clinically well may

continue on therapy following RECIST progression with new lesions or increase in target lesions if the increase in disease burden does not meet the definition of iCPD by immune response criteria [24] outlined in [section 11.5](#).

After removal for disease progression, patients should be followed for survival per the study calendar ([Section 5.0](#)).

